The central hypothesis tested in this study is whether a 4-day antibiotics course is equivalent to an 8-day course for post-drainage primary and secondary clinical outcomes.

Primary outcomes:

- readmission rate

Secondary Outcomes:

- length of stay (LOS)
- rate of post-drainage surgical site infection until 30 days after discharge
- rate of post-drainage abdominal abscess until 30 days after discharge
- secondary site infections

C. Methods

C.1. Study Design

This research proposes a randomized, prospective, equivalence trial design to test the research hypothesis. This study will demonstrate no difference in clinical outcomes between the 4-day antibiotic course and the 8-day course. The study will include 342

IRB#: 17-055

Title: A prospective randomized trial of antibiotic duration in post-appendectomy abscess

PI: [name]

Col's: [name], [name]; [name]; [name]; [name]; [name]; [name]; [name] [name]; [name]; [name].

pediatric patients (includes 10% oversampled) ages 2 through 17 years treated from February 1, 2019 onward until the study cohorts have been filled. This study is based on an expectation of 90% success (10% readmitted) in arm A=10% and expectation of 90% success (10% readmitted) in arm B =10%. The clinical difference in primary outcome between the two groups that we are prepared to accept is equal or greater than 10% (i.e., clinically, we are willing to accept 10 children per 100 who may have benefited from the long course but received a short course to achieve 90% of children who received the short course and would not have benefitted from a long course). The sample size needed to attain a power of 0.80 at alpha=0.05 is 342 (171 in each arm, which includes a 10% attrition rate). The risk of type I error is 1-0.95 (alpha=0.05); power=0.80. The study will proceed until 171 patients are consented for each arm. Study personnel will perform an interim analysis of the data approximately halfway through study enrollment.

Definition of perforated appendicitis - Perforated appendicitis is defined as a visible hole or feces found in the abdomen at laparoscopy. ***For purposes of research, either the hole or feces is photographed, and "hole," "feces/stool in the abdomen," or other note describing perforation will need to be specifically described in the operative report.***

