Col's: [name], [name]; [name]; [name]; [name]; [name]; [name]; [name] [name]; [name]; [name].

It is estimated that it will take about 6 years for PCH to fill the study arms; interim analysis will be performed when study cohorts are half-filled. In order to complete this and other planned pediatric appendicitis studies more quickly, we are planning to add other study sites through the Western Surgical Research Consortium. The multisite approval process will be facilitated by Streamlined Multisite Accelerated Resources for Trials (SMART) IRB certification. With participation from the nine hospitals in the Western Surgical Research Consortium, we would expect to fill the trial cohorts in approximately 2 years.

C.4. Data Analysis Plan

The study will describe patient and clinical characteristics related to laparoscopy among study cohorts (e.g., age, BMI, gender, maximum temperature upon admission, diarrhea at presentation, duration of symptoms, and white blood cell count); patient recovery and abscess formation (e.g., time to abscess, abscess size if available, time to regular diet, and LOS after the drainage); primary clinical outcome (readmission); and secondary clinical outcomes (LOS, total visits after discharge, post-drainage occurrence of abscess, and post-drainage secondary infection).

All data will be described using descriptive statistics, including means, standard deviation, and proportions. Differences among treatment cohorts and on clinical outcomes will be assessed using parametric and non-parametric tests as appropriate. Factors confounding outcomes will be identified *a priori* from research and empirically via correlational analysis for continuous measures or through non-parametric techniques for discrete variables with a Bonferroni correction for multiple comparisons among families of statistical tests. Binomial logistical regression will also be used where appropriate. Unadjusted odds ratios will be used to identify variables of interest and confounding effects for discrete dependent variables of interest. Adjusted odds ratios will be used to compare differences among study cohorts and covariates (e.g., age, gender, white blood cell count, and BMI), interactions, and confounders as appropriate. Statistical significance will be defined as an alpha of 0.05, with two-sided alternative hypothesis and a Bonferroni correction for multiple comparison. Data analysis will be performed using SPSS and R.

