Interim Analysis - At approximately the halfway point of the study (i.e., 171 patients per arm), study personnel will undertake an interim analysis.

IRB#: 17-055

Title: A prospective randomized trial of antibiotic duration in post-appendectomy abscess

PI: [name]

Col's: [name], [name]; [name]; [name]; [name]; [name]; [name]; [name] [name]; [name]; [name].

D. Benefit and Risk Assessment

D.1. Risk Assessment:

This study poses minimal risk. There are no additional expected risks of this study related to the trial protocol. The study protocol aligns to the current hospital standard of care at diagnosis, treatment, and discharge. This study excludes any patient who possesses a higher than normal risk of abscess formation. The study also excludes any patient the surgeon believes should NOT participate for any reason.

Hospital standard of care currently diagnoses acute perforated appendicitis via laparoscopy, which minimizes the risk of over-inclusion (e.g., including a patient who does not have perforated appendicitis and post-appendectomy abscess). Photographing at laparoscopy when possible also minimizes risk of inadvertent exclusion because patients may be asymptomatic for perforation at the time of laparoscopy. The engagement and involvement of pediatric surgeons (multiple surgeons at each institution when possible) will assure patient safety during the trial. Physician training on the protocol will also contribute to study safety and consistency. Finally, we will also follow strict study oversight protocol, including adverse event reporting and in accordance with Good Clinical Practices (GCP) research guidelines.

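### The only numeric trigger for the halfway interim, 171 patients per arm, is full enrolment; the look also has no stated decision criterion or alpha

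*Combined protocol and SAP*

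**What the plan says.** The combined protocol and SAP times the interim analysis in three places.

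- C.1, Study Design: "Study personnel will perform an interim analysis of the data approximately halfway through study enrollment".
- C.3, Data Collection: "interim analysis will be performed when study cohorts are half-filled".
- C.4, Data Analysis Plan, Interim Analysis: "At approximately the halfway point of the study (i.e., 171 patients per arm), study personnel will undertake an interim analysis".

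C.1 gives the sample size as 342, or 171 in each arm including 10% attrition, and fixes the end of enrolment: "The study will proceed until 171 patients are consented for each arm".

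C.3 gives two accrual estimates. For the lead hospital alone, "It is estimated that it will take about 6 years for PCH to fill the study arms". With the nine consortium hospitals, "we would expect to fill the trial cohorts in approximately 2 years".

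D.1, Risk Assessment, lets the principal investigator and study investigators decide together whether interim results support closing the study, completing it or adding an arm. It adds that a no-antibiotic arm is under consideration if the study succeeds.

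The general significance rule in C.4 reads: "Statistical significance will be defined as an alpha of 0.05, with two-sided alternative hypothesis and a Bonferroni correction for multiple comparison". It does not mention interim looks. The other Bonferroni reference in C.4 concerns the identification of confounders.

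**The concern.** The number attached to the halfway look is the number at which enrolment ends. A team working from the analysis plan alone would hold the look until the last patient had been consented. An interim that can close a trial or add an arm is useful only while patients are still to be enrolled, so the literal trigger removes its purpose for the two planned arms.

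There is a second, lesser gap. D.1 lists actions and decision-makers, but no section names the endpoint to be examined, the result that would lead to each action, or how alpha is handled. In an equivalence trial this leaves open whether a non-significant difference, or an early equivalence result, could be acted on at half the data.

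**Working it through.** **1. The plan's own sample size.** Inputs from C.1: 10% readmission in both arms, a 10-point margin, alpha 0.05, power 0.80 and 10% attrition. Two one-sided tests (TOST), each at one-sided 0.05, with true difference zero:

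n per arm = 2p(1−p)(z₀.₉₅ + z₀.₉₀)² / margin² = 2 × 0.1 × 0.9 × (1.645 + 1.282)² / 0.1² = 154.1, rounded up to 155.

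155 × 1.10 = 170.5, rounded up to 171 per arm, or 342 in total. The stated figure is reproduced, so 171 per arm is the full planned arm size.

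**2. The trigger as a fraction of enrolment.**

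- As written in C.4: 2 × 171 = 342, and 342/342 = 100%.
- True halfway: 342/2 = 171 in total, and 171/2 = 85.5, about 86 per arm.

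**3. The delay if the literal trigger is followed, with even accrual.**

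- Nine hospitals, 2 years: 342/24 = 14.25 patients a month. Halfway is 171/14.25 = 12 months and full enrolment is 24 months, so the look is 12 months late.
- Lead hospital alone, 6 years: 342/72 = 4.75 a month. Halfway is 36 months and full enrolment is 72 months, so the look is 36 months late. C.3 plans to add the other sites, so the 12-month figure is the relevant one.

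**4. Illustration of why the missing criterion matters.** The documents state neither of the rules below. They show only what is left open. Looks are taken at 77 then 154 per arm (after 10% attrition: 171 × 0.9 = 153.9) or at 86 then 171 per arm (no attrition).

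| Assumed rule | Final look only | With a halfway look |
|---|---|---|
| Equivalence may be claimed at either look: TOST, 10-point margin, one-sided 0.05, unpooled Wald. False equivalence at true 10% v 20% (2,000,000 simulated trials) | about 5.3% | 7.1% (77/154) to 7.8% (86/171) |
| A non-significant two-sided 0.05 difference test is read as no difference. Chance of missing a true 10% v 20% (exact binomial, pooled z) | 30% (154), 25% (171) | 58% (77), 55% (86), at the halfway look |

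With both arms truly at 10%, the exact chance that TOST shows equivalence is 0.33 at 77 per arm and 0.43 at 86 per arm, against 0.79 at 154 per arm.

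**The case against.** The strongest reply on the trigger is that this is a clerical slip. All three timing statements say halfway, and only one parenthesis disagrees. A sensible team would follow the majority and the delay would never occur. Most of that stands: the intended timing is clear, and the 12 months arise only if the parenthesis is followed. But approximately halfway cannot stretch to 100%, and the parenthesis is the only count in the document that staff could act on. It sits in the analysis plan itself.

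On the missing criterion, the reply is that the look may be meant as descriptive or for safety. D.1 refers to a "strict study oversight protocol, including adverse event reporting", and with no equivalence claim at the interim there is no inflation from that source. That also stands, as far as it goes. Adverse event reporting is oversight, however, and does not say what interim result would lead to closing the study or adding an arm.

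A reader might infer from the table above that the trial has a false-equivalence rate of 7–8%, or that it will stop wrongly more than half the time. The documents do not support that, because no section permits an equivalence claim at the interim or makes a non-significant difference a reason to close. A reader might also infer that a third arm would take patients from the two planned arms. The documents give no allocation for such an arm, and the wording about a no-antibiotic arm can be read as a later proposal, so no power loss can be derived.

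**Conclusion.** The trigger is wrong as written. It equals 100% of planned enrolment and contradicts C.1, C.3 and its own sentence. This rests only on figures in the document and is certain. The consequence, a look about 12 months late that cannot affect enrolment to the two planned arms, assumes that the parenthesis is followed literally and that accrual is even over the 2-year plan.

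The lack of a criterion linking results to actions, and of any alpha treatment for the look, is a gap in specification and not a demonstrated error rate. It supports a recommendation to add text. The illustrative probabilities show that the choice of rule matters; they do not describe what this trial will do.

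The point should be fixed, with the corrected figure first and the added sentence second.

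**What to change.** **Correction.** In C.4, Interim Analysis, change the parenthesis to read *171 patients in total, about 86 per arm*. This agrees with C.1 and C.3 and has no statistical cost.

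**Recommendation.** Add a sentence such as: *Neither equivalence nor no difference will be concluded from the interim analysis; the look therefore spends no alpha for the equivalence claim, and the Bonferroni correction in this section does not apply to it.* Name the endpoint to be examined. Any threshold for closing the study is for the sponsor to set before the look.

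**Cost.** One figure and about two sentences, with no change in sample size. The option to claim equivalence early is lost, but with both arms at 10% readmission it would succeed only about 33% (77 per arm) to 43% (86 per arm) of the time.

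**Alternative.** If an early claim is wanted, specify an alpha split in advance. For example, an O'Brien-Fleming split of one-sided 0.0088 then 0.0467 keeps false equivalence at about 5%, with power 0.786 against 0.794 for a single final look at 154 per arm.

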Based on estimates from the Division of Pediatric Surgery, PCH performs approximately 1000 laparoscopic appendectomies annually. Approximately one-third of these appendectomies (300) are perforated; about 10%-20% of these 300 perforated patients (30-60) will develop a post-surgical abscess treated with a percutaneous drain and IV antibiotics.

Screening - The study population is comprised of patients who, upon admission, are diagnosed with perforated appendicitis and who, after laparoscopy, form an abscess (while still in hospital or discharged and then readmitted with abscess), and are treated with percutaneous drainage and IV ceftriaxone/metronidazole or other broad spectrum antibiotic equivalent per hospital standard of care. Screened patients will be assigned a screening ID, which will be maintained in a screening log.

Randomization - Once eligibility for study inclusion is determined at the time of drainage, the patient will be consented by the principal investigator or sub-investigator and assigned a study number. A block randomization strategy will be used based on a random number generator and applied after consent by site to assign patients to either the control (8-day) or experimental (4-day) arm of the study. All patients will be randomly assigned by patient study numbers. A current randomized trial underway at Phoenix Children's Hospital requires photography to confirm a diagnosis of perforation (IRB 17-011). We propose to follow the same approach for verifying perforated appendicitis across WSPRC institutions in this study. When possible, the hole or feces will be

IRB#: 17-055

Title: A prospective randomized trial of antibiotic duration in post-appendectomy abscess

PI: [name]

Col's: [name], [name]; [name]; [name]; [name]; [name]; [name]; [name] [name]; [name]; [name].

photographed. If not, "hole," "feces/stool in the abdomen," or other note describing perforation will need to be specifically described in the operative report. The two study arms will include some patients with abscess that has been confirmed though CT or ultrasound as part of standard of care prior to study participation. We will include CT/ultrasound results as part of data collection.

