Antibiotic regimen - All post-laparoscopic abscess patients will receive the standard of care for antibiotic therapy—IV ceftriaxone/metronidazole or other broad spectrum antibiotic equivalent—until afebrile (38.5° C) and tolerating food for 24 hours (i.e., without vomiting). CBC panels are also standard of care and may be drawn multiple times during the patient's stay. Standard of care at discharge includes prescribed oral, empiric, antibiotic therapy (PO), such as ampicillin/clavulanate or other broad spectrum antibiotic. The choice and the duration of broad spectrum antibiotic prescription are at the surgeon's discretion.

In this study, all patients will be treated with the hospital standard of care and receive in-patient treatment for abscess until afebrile and tolerating food for 24 hours. After percutaneous drainage of the abscess, the patient will be randomly assigned to receive either an 8-day regimen (arm A) or a 4-day regimen (arm B) of antibiotics (Diagram 1). Patients will remain on IV ceftriaxone/metronidazole or other broad spectrum antibiotic equivalent until afebrile and tolerating food for 24 hours. Patients will complete their assigned 4- or 8-day regimen with oral ampicillin clavulanate or other broad spectrum antibiotic equivalent. If patients are not afebrile at the completion of their assigned regimen, prescribing an extended course of antibiotics is at the discretion of the treating surgeon. A prescribed oral course of antibiotics may be finished in the hospital or at home if patient is discharged.

Ampicillin and clavulanate have been safely utilized in previous pediatric research.^{5,10,14,11} These antibiotics have demonstrated clinical equivalence in both retrospective studies and prospective trials.^{9,11} This randomized trial is the first to address duration of antibiotic treatment in pediatric patients diagnosed with perforated appendicitis and who form a post-laparoscopic abscess. Pediatric patients who are allergic to ampicillin will be prescribed another broad-spectrum antibiotic (e.g., gentamycin/clindamycin or ciprofloxacin) at the discretion of the treating surgeon.

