Two arms are proposed for the study following the protocol implemented for adults in a recent randomized trial.²¹ In the control arm, patients will be treated with an 8-day course of antibiotics, and in the experimental arm, patients will be treated with a 4-day course of antibiotics. The randomized trial should control for all confounding effects. In addition,

IRB#: 17-055

Title: A prospective randomized trial of antibiotic duration in post-appendectomy abscess

PI: [name]

CoI's: [name], [name]; [name]; [name]; [name]; [name]; [name]; [name] [name]; [name]; [name].

we will collect clinical data on the pre-operative, peri-operative and post-operative antibiotic treatment and number of days on antibiotic therapy prior to discharge to manage this potential confounder *post hoc*.

There is a low probability of study attrition or loss to follow-up. As the primary treatment provider in a study with a short (30-day) follow-up period for readmission, we do not expect significant attrition. Follow-up will entail tracking all patients from the initial study who return to the hospital for complications related to the procedure within 30 days of discharge. All complications, including those requiring readmission, will be included in the follow-up. All study patients will be assessed for primary and secondary clinical outcomes. Complications associated with surgically treated acute appendicitis based on the National Surgery Quality Improvement Program criteria (available at <http://nsqip.healthsoftonline.com/hsi/>) include (1) wound infection, (2) abscess, (3) post-discharge small bowel obstruction, (4) hernia, (5) length of hospital stay of greater than 4 days, and (6) death.

[figure not shown]
IRB#: 17-055

Title: A prospective randomized trial of antibiotic duration in post-appendectomy abscess

PI: [name]

CoI's: [name], [name]; [name]; [name]; [name]; [name]; [name]; [name] [name]; [name]; [name].

Diagram 1: Treatment arms for randomized trial of an 8-day antibiotic treatment vs. 4-day treatment of post-laparoscopic abscess formation in pediatric complicated (perforated) appendicitis.

* If febrile after assigned course of antibiotics (i.e., 8 days or 4 days) is completed, extended antibiotic treatment will be up to the treating surgeon.

†Patient may be discharged before 8- or 4-day course is completed and may finish antibiotics at home.

IRB#: 17-055

V5 9/25/2019

IRB#: 17-055

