This study does not require new or unique diagnostic procedures other than those already in use under hospital standard of care. In this study protocol, there are no changes to the standard of care for treatment of post-laparoscopy abscess formation—which currently includes IV antibiotics and percutaneous drainage until afebrile and tolerating food intake for at least 24 hours—and then discharge to home with an oral antibiotic. All study patients receive the standard of care until afebrile and eligible for discharge to home. At discharge, standard of care requires attending physicians to determine the regimen for patients who have received treatment for post-appendectomy abscess. The principal investigator, [name], along with other study investigators and research coordinators, will provide study oversight. He and the study investigators will also jointly determine if interim analyses support closing the study, completing the study, or adding another study arm. Specifically, study investigators are considering proposing no antibiotic at drainage if this study is successful.

As with any data collection, there is a risk of breach of confidentiality and protected health information (PHI). This risk will be minimized by the following measures:

IRB#: 17-055

V5 9/25/2019

IRB#: 17-055

Title: A prospective randomized trial of antibiotic duration in post-appendectomy abscess

PI: [name]

Col's: [name], [name]; [name]; [name]; [name]; [name]; [name]; [name] [name]; [name]; [name].

- 1) Subject identity will be protected and kept confidential by storing all research records in a password-protected file on a HIPAA-compliant, cloud-based server (REDCap), with access limited to study personnel;
- 2) Subject informed consent/assent statements will include detail on confidentiality and protection of confidential health records;
- 3) The compiled data used for analysis will have limited PHI and will not be directly linkable to individual subjects;
- 4) Manuscripts prepared for presentation and journals will be aggregated and will not contain any individual PHI or identifiable patient data.

D.2. Benefits Assessment:

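### Investigators who enrol and treat the children also act on the interim results, with no limit on who sees arm-level data, so later conduct could be influenced in an uncertain direction

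*Combined protocol and SAP*

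**What the plan says.** **Who runs and acts on the look.** C.1 and C.4 have study personnel perform the interim analysis. D.1 then says of the principal investigator: "He and the study investigators will also jointly determine if interim analyses support closing the study, completing the study, or adding another study arm". The next sentence of D.1 adds that "study investigators are considering proposing no antibiotic at drainage if this study is successful".

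**Who enrols and treats.** Under Randomization in C.1, "the patient will be consented by the principal investigator or sub-investigator and assigned a study number"; E.3 has the pediatric surgeon consent families. On follow-up, C.1 states: "As the primary treatment provider in a study with a short (30-day) follow-up period for readmission, we do not expect significant attrition". C.2 also lets the surgeon keep any patient out of the trial for any reason.

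**What remains open to judgement.** Under Antibiotic regimen in C.1, "the patient will be randomly assigned to receive either an 8-day regimen (arm A) or a 4-day regimen (arm B) of antibiotics". For a child who is not afebrile when the assigned course ends, "prescribing an extended course of antibiotics is at the discretion of the treating surgeon". Readmission is the primary outcome (sections B and C.4), and no criteria for it are given.

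**What is not described.** The plan describes no masking of clinicians, families or outcome assessors, no reviewer of the interim results outside the study team, and no restriction on access to results by arm. The only oversight that D.1 names is by the principal investigator, other investigators and coordinators, together with adverse event reporting under GCP.

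**The concern.** The people who decide what the interim results mean overlap with those who enrol and treat. Four days against eight without placebo is apparent to everyone at the bedside, and the primary endpoint is itself a clinical decision. An investigator who has seen readmission by arm could, without any intent, change whom to approach, how readily to extend a course in a child who still has fever, or how readily to readmit. Where the short course is truly worse, anything that draws the recorded rates together favours a claim of equivalence. The same investigators have a stated next step, a no-antibiotic regimen, that depends on the study succeeding. D.1 therefore states a rule that opens a route for bias, and the route can be closed with wording.

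**Working it through.** **1. The plan's own sample size.** Inputs from C.1: 10% readmission expected in each arm, a 10-point margin, alpha 0.05, power 0.80 and 10% added for attrition. With two one-sided tests at 0.05 each:

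n = [0.10×0.90 + 0.10×0.90] × (1.645 + 1.282)² / 0.10² = 0.18 × 8.564 / 0.01 = 154.1, so 155 per arm.

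155 × 1.10 = 170.5, so 171 per arm and 342 in total. The stated figure reproduces, and it is not in dispute. It fixes the analysis used below: 155 evaluable per arm, with equivalence claimed if the 90% interval lies within ±10 points.

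**2. Assumptions that are not in the documents.** True readmission is 10% (8-day) and 20% (4-day), which is on the margin, so any claim of equivalence is false. The look falls after 78 children per arm and 77 per arm follow. A reassuring look is an observed difference (4-day minus 8-day) of 5 points or less. After such a look a fraction f of 4-day readmissions is avoided; after any other look nothing changes.

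**3. Calculation.** The later 4-day rate is 0.20 × (1 − f) after a reassuring look and 0.20 otherwise. Equivalence is claimed if d ± 1.645 × SE lies within ±0.10, where d is the observed difference at the end and SE = √[pA(1−pA)/155 + pB(1−pB)/155] with observed proportions. Exact binomial probabilities are summed over all interim and later counts. A reassuring look occurs in about 16% of trials. Without influence, 77 × 0.20 = 15.4 later 4-day readmissions are expected, so f = 10%, 25% and 50% correspond to about 1.5, 3.9 and 7.7 children.

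| Fraction avoided, f | Only after a look of 5 points or less (about 16% of looks) | Only after a look of 0 or less (about 5% of looks) | After every look |
|---|---|---|---|
| 0 | 5.3% | 5.3% | 5.3% |
| 10% | 7.1% | 6.0% | 8.6% |
| 25% | 10.5% | 6.9% | 16.3% |
| 50% | 15.2% | 7.4% | 37.6% |

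The second column matches the mechanism described. The last column does not: it has clinicians avoiding readmission even after a look showing the short course doing badly, and under these assumptions most looks do show that.

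**4. Direction.** Two checks with the same method show that the effect can go the other way.
- If both true rates are 10%, avoiding half of later 4-day readmissions after every look pushes the arms apart and lowers the chance of claiming equivalence from about 80% to 75%.
- At 10% against 20%, if clinicians readmit 4-day children 25% more readily after looks above 5 points, false equivalence falls from 5.3% to 4.1%.

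**5. Timing.** C.1 puts the look about halfway through enrolment, and C.3 puts it when the cohorts are half-filled. The interim paragraph of C.4 also says halfway but glosses this as 171 patients per arm, which is the full target. The illustration needs the half-enrolment reading.

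**The case against.** Much can be said for the plan.

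- Extension is limited to children who are not afebrile at the end of the course, and discharge is tied to being afebrile and tolerating food for 24 hours. Neither is free discretion. This stands, and it leaves enrolment and readmission as the more open routes.
- The documents do not say who decides readmission, that the treating surgeon is a study investigator, or that every site surgeon sees rates by arm. They also do not say in terms that the trial is unmasked or that the interim is a comparison by arm. These are inferences: from the primary-provider role, from the visible durations without placebo, and from an interim that can close the study or add an arm. They are reasonable, but they are not text.
- Clinicians know the arm from the first day, and restricting interim results does not change that. This stands too. The fix removes only the additional influence of knowing how the arms compare.
- On the literal count in C.4, enrolment would already be complete at the look, with little left to influence. The other two statements say half, so the point survives, but it depends on that reading.

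A reader might infer that interim access will pull the arms together and that false equivalence could approach 38%. The documents do not support this: the figure requires avoidance after every look, and the direction is not fixed. A reader might also infer that adding an arm should be struck from the interim decisions because success is known only at the end. D.1 lets the interim support closing the study, so success may refer to the interim itself. Removing that option would be a design preference and does not follow from who sees the results.

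**Conclusion.** The point holds as a risk of bias of uncertain direction that the plan should close; no bias is demonstrated. The overlap between those who act on the interim results and those who consent children is explicit in D.1 and C.1. The overlap with treatment rests on the team's description of itself, and the overlap with readmission decisions is inferred.

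The size is illustrative: false equivalence of about 7%, 10% or 15% in place of about 5%. It rests on assumed true rates of 10% and 20%, 155 evaluable per arm, a look at half enrolment, a 5-point definition of reassuring, and each one-sided test at 0.05. C.4 mentions a two-sided 0.05; if each side were tested at 0.025, the starting error would be about 2.6%. A stricter definition of reassuring shrinks the effect to between 6% and 7%. The change is worth making because it costs little, although the likely effect is modest.

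**What to change.** In C.4 and D.1, state that:

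1. Trauma Research, which under E.1 already collects the data and downloads them for analysis, prepares the arm-level interim results.
2. These results are seen only by personnel already available who do not enrol, treat or readmit trial patients. They are to be listed in the approved IRB application, because E.4 restricts data sharing to listed individuals.
3. Investigators and sites are told only the decision to continue or stop.

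Reconcile the interim timing in C.1, C.3 and C.4, so that it is clear whether the look falls at half enrolment or at 171 per arm.

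The cost is protocol wording and possibly a minor update to the IRB listing. No new panel needs to be recruited, and the sample size and treatment rules are unchanged. The downside is small: investigators give up sight of results by arm until the end of the trial.
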